**Estimated Study Duration:**

Outcome Measures:	Study Aim 1 (Between- Group Differences)
	
 
• Primary Clinical Endpoints 
 
○ A difference in the change in pain scores over time from baseline to month 12 (M12) as measured by the Numerical Pain Score (NPS)
 
○ A difference in the change in depression scores over time from baseline to M12 as measured by the Patient Health Questionnaire (PHQ-9)
 
○ A difference in the change in pain medication use over time from baseline to M12, calculated as mean daily morphine equivalents (MEQs)
 
 
 
• Secondary Clinical Endpoints 
 
○ A difference in the change in physical function/disability over time from baseline to M12 as measured by the Oswestry Disability Index (ODI)
 
 
 
• Endpoints Related to Resource Utilization 
 
○ A difference in the change in healthcare resource utilization over time (quarterly) from baseline to M12: number of hospitalizations, emergency department (ED) visits, inpatient, outpatient visits, rehabilitation visits, and pharmacy/medication orders
 
○ A difference in the change in healthcare costs over time (quarterly) from baseline to M12: total, inpatient, outpatient, rehabilitation, and pharmacy
 
 
 

	Study Aim 2 Comparisons within WHT Group
Sample Size:	
 
• Sleep: change in number of hours and number of restful hours per night over time from month 1 (M1) to M12
 
• Activity level: change in number of steps and minutes of exercise per day over time from M1 to M12
 
• Daily pain scores: change in worst pain of the day (mean value for the month), number of episodes of breakthrough pain (episodes per 7 days), and mean level of breakthrough pain (mean value for month) over time from M1 to M12
 
 
Sample size estimated to be at least 240 WHT patients, 1000 MPM patients, and 150 historic MPP patients. Based on these sample sizes, and assuming a 10% drop-out rate, detectable effect sizes at 80% power for the primary clinical outcomes as analyzed by repeated measures analysis of variance (ANOVA) model and using an omnibus F test (difference in changes between the groups at any time) are:
 
 
• NPS: 0.35 versus MPM; 0.42 versus historic MPP
 
• PHQ-8: 1.40 versus MPM; 1.81 versus historic MPP
 
• MEQs: 11.51 versus MPM; 17.58 versus historic MPP
 

Statistical Methods:	
For clinical outcomes (primary, secondary, and exploratory), the effects of WHT will be quantified by calculating the change from baseline in clinical outcome variables in the WHT group over 12 months. For primary and secondary outcomes that are measured in the WHT group plus at least 1 control group, generalized linear modeling or nonparametric methods (depending on the score distributions) will be used to compare outcomes across the cohorts. Patient demographic and clinical characteristics that differ between groups at baseline will be included in multivariate adjusted models.
 
Repeated measures models will be used to generate point estimates and 95% confidence intervals (CIs) for least square mean (LSM) differences, odds ratios (ORs), or risk ratios (RRs). Where appropriate an overall F statistic will be generated to compare the change in groups across the study period (interaction of group*time).
 
For the analysis of healthcare utilization, a log-link function with a Poisson or negative binomial distribution will be used. For cost outcomes, a log-link function with a gamma distribution will be used. Otherwise, the same techniques described above (eg, GLM methods to account for matched groups, estimates, and CIs) will be used.
 
For analysis related to clinical outcomes collected only in the WHT group, the effects of WHT will be quantified by calculating the change from baseline over 12 months and using repeated measures ANCOVA models to compare to the null hypothesis (0 change).

-----------------------------	---

**Date of Protocol:** 12 September 2017

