## Protocol Synopsis

**Protocol  
Number:**

2017-0196

**Title:** Effect of Wearable Health Technology on Patients Treated for Chronic Pain at Geisinger Health System

**Sponsor:** Purdue Pharma L.P.  
[name]  
[name]  
[name]

**Study Phase:** Phase 4

**Study Sites:** The study will be conducted in the United States at 1 site, the Multidisciplinary Pain Program at Geisinger Health System

**Indication:** Chronic Pain

**Background:** Care for the chronic pain patients can be challenging. Providers are dependent on patients' recall of their symptoms between visits to gauge disease severity and treatment progress. Providers often lack timely access to patients' data on symptom severity, thereby limiting the providers' ability to effectively manage and optimize long-term treatment regimens for their patients.

Recent use of wearable health technology (WHT) has been effective in improving patient outcomes. Many wearable biosensors and their applications have been introduced in different stand-alone or interactive formats. WHT apps may have interactive capabilities involving active health or behavior change information that collects data from the user. WHT can detect abnormal and unforeseen situations and monitor physiological parameters and symptoms through these trackers. This technology has transformed healthcare by allowing continuous monitoring of patients without hospitalization. Medical monitoring of patients' body temperature, heart rate, brain activity, muscle motion and other critical data can be delivered through these trackers. When integrated with an expert-directed chronic pain intervention program like Geisinger's Multidisciplinary Pain Program (MPP), WHT (eg iPhone, Apple Watch) may improve comprehensive patient management and outcomes for patients living with chronic disease. WHT can also provide real-time data, allowing a healthcare provider to engage in more proactive patient care.

**Objectives** To assess whether the addition of WHT to the Geisinger MPP leads to improvements in clinically meaningful patient outcomes, reductions in healthcare utilization and costs.

**Patient Population:** The study population will be adult ( $\geq 18$  to  $< 76$  years) chronic pain patients being treated at pain clinics in the Geisinger healthcare system.

There will be 3 study groups, a WHT treatment group, a concurrent Medical Pain Management (MPM) control, and an historic MPP control:

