1. WHT treatment group: patients admitted to the MPP during a predefined 12-month period who consented to participate in the study.
2. MPM control group: patients from MPM clinics within Geisinger during the same 12-month period.
3. Historic MPP control group: patients who completed the MPP 12 months before the start of this study (ie, before WHT was introduced to the MPP in August 2017).

**Study Design:** This is a prospective, non-randomized, non-blinded trial with historic and concurrent controls to assess the effect of the addition of WHT (Apple Watch, iPhone, Pain App, and physician and patient dashboards) on patient and health system outcomes. The WHT intervention group will include patients enrolled in the Geisinger's MPP Program over 1 year, with 1 year of follow up. Patients in the WHT group will be compared to patients in 2 control groups: patients enrolled in the MPP in the preceding year (historic control group), and patients enrolled on the MPM over the same period (concurrent control group).

The WHT intervention will consist of the following:

- Patient and HCP tracking of patient-reported pain, pain management, disability, depression and medication usage over time
- Patient and HCP tracking of quality of sleep and activity over time
- Prompts to patients to engage in self-care, including non-pharmaceutical pain management therapies consistent with their MPP training
- HCP alerts if patients exceed pre-specified thresholds in pain or functioning

Patients will use the WHT 20 hours per day, every day for a period of 12 months.

Patients will attend study visits at baseline and months 2, 4, 6, 8, 10 and 12. Patients consented into the WHT group will participate in the study for 12 months from the day of enrollment.

Outcome data for control patients will be collected retrospectively from the electronic health record (EHR). Assessments will have occurred as part of their standard of care.

Twelve months of enrollment, with 12 months of follow-up, for a total of 24 months.

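### The cost endpoint names no component for the WHT package and leaves total cost undefined, although the objective is whether adding WHT reduces costs

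*Combined protocol and SAP*

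**What the plan says.** All references are to the Protocol Synopsis in the Combined protocol and SAP.

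- **Objectives.** The question is whether adding WHT to the pain programme "leads to improvements in clinically meaningful patient outcomes, reductions in healthcare utilization and costs".
- **Study Design.** The trial assesses "the effect of the addition of WHT (Apple Watch, iPhone, Pain App, and physician and patient dashboards) on patient and health system outcomes". The intervention also has a clinician side, including "HCP alerts if patients exceed pre-specified thresholds in pain or functioning". On exposure: "Patients will use the WHT 20 hours per day, every day for a period of 12 months".
- **Outcome Measures, Endpoints Related to Resource Utilization.** The cost endpoint is "A difference in the change in healthcare costs over time (quarterly) from baseline to M12: total, inpatient, outpatient, rehabilitation, and pharmacy".
- **Statistical Methods.** "For cost outcomes, a log-link function with a gamma distribution will be used". This section says nothing more about how costs are built up.

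The synopsis does not define the total, state a costing perspective or name unit costs. It does not say who pays for the WHT, or whether its cost is included, excluded on purpose or reported separately.

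**The concern.** The objective attributes a possible cost reduction to adding WHT, but the endpoint that answers it has no line for what is added. Devices, app, dashboards and the time clinicians spend on alerts do not belong naturally under pharmacy, rehabilitation, outpatient or inpatient care.

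If an analyst forms the total from those four categories, which the plan permits, the between-group difference omits an item that only the WHT group incurs. The sign of the cost conclusion is then at stake: a modest measured saving in care could be smaller than the cost of the package that produced it. With the total undefined, the choice of what it includes could also be made after the results are seen.

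**Working it through.** The plan states no cost figure, so there is none to reproduce. Its detectable differences concern pain, depression and morphine equivalents and do not bear on cost. The check sets the sections side by side and then uses simple accounting.

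**1. Is the WHT cost placed anywhere?** Study Design lists a watch, phone, app, two dashboards, and clinician tracking and alerts. Outcome Measures lists a total and four care categories. Statistical Methods gives a model only. No section assigns the package to a category or adds one for it.

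**2. Does it arise in one group only?** The historic controls completed the programme before WHT was introduced in August 2017. The concurrent controls come from other clinics, and nothing says that they receive WHT. So the package cost is C per patient in the WHT group and 0 in both control groups.

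**3. Does the design remove it?** No. WHT is used during the same 12 months that the cost endpoint covers, so measuring change from baseline does not cancel it. Adjusting for baseline characteristics does not either, because C is part of the intervention.

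**4. Effect on the conclusion.** Let S be the per-patient saving in the listed categories.

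- Reported saving = S
- Net saving = S − C

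The sign reverses whenever 0 < S < C. With assumed S = 500 USD and C = 1,000 USD, the report shows a saving of 500, while the net is 500 − 1,000 = −500, an increase of 500.

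**5. Scale, under assumed prices.** Input from Sample Size: 240 WHT patients. Assumed: C = 250 to 2,000 USD over 12 months.

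- All patients: 240 × 250 = 60,000; 240 × 2,000 = 480,000 USD
- Per patient per quarter: 250/4 = 62.50; 2,000/4 = 500 USD
- Without the 10% assumed to drop out: 240 × 0.9 = 216; 216 × 250 = 54,000; 216 × 2,000 = 432,000 USD

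If listed-category costs are further assumed to be 10,000 to 20,000 USD per patient-year, C is between 250/20,000 = 1.25% and 2,000/10,000 = 20% of them. A 5% saving would be 500 to 1,000 USD. It is cancelled at C = 500 if care costs 10,000, and at C = 1,000 if care costs 20,000.

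**6. On the scale of the planned model.** A log link gives a ratio of means. Ignoring baseline terms, let r = (WHT mean)/(control mean M). Including the package changes the ratio to r + C/M. With assumed M = 10,000, r = 0.95 and C = 1,000, it becomes 0.95 + 0.10 = 1.05, the same reversal as in step 4. Netting off afterwards therefore has to be done on the estimated difference in mean dollars, not on the ratio itself.

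**7. An item in the other direction.** WHT patients attend seven study visits (baseline and six more through month 12), whereas control assessments come from standard care. Let V be the cost of the visits made only because of the protocol. If these are counted as outpatient cost, the reported saving is S − V. If they are research cost and not part of the intervention, reported minus net is (S − V) − (S − C) = C − V, which can have either sign.

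**The case against.** Five points can be made against the concern.

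- **The total is undefined, not defined as excluding WHT.** It stands beside four categories and is nowhere said to be their sum. A reader might infer that the plan leaves the WHT cost out. The text supports only that no WHT component is specified and none is required. This stands, and the point is worded accordingly.
- **The cost of care consumed is a legitimate target.** The endpoint is headed as healthcare cost, under resource utilisation, and the plan promises no net-cost or cost-effectiveness result. For that target, leaving out the devices limits what may be concluded and is not bias. This also stands, provided that the perspective is declared and the conclusion is limited to match. The available text does neither.
- **The net direction is not fixed.** A reader might infer that the contrast must favour WHT by the full package cost. That is the effect of this one omission alone. Protocol-driven visits could work the other way. The contrast with the concurrent clinics also mixes in the pain programme itself, so the historic contrast comes closer to isolating WHT.
- **Premises about billing are outside the documents.** They do not say who supplies the devices, whether costs come from billing data or how alert work is recorded. Visits or medication orders that follow an alert would fall into the existing categories. The concern is limited to the package and the monitoring time.
- **Only a synopsis is available, and the harm is recoverable.** A fuller text might define the costing, and a fixed cost per patient can be set against the estimate at reporting. Both are fair, and they explain why the remedy is small. They do not remove the case for settling the definition before results are known.

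**Conclusion.** The point holds in a limited form. The cost endpoint specifies no component for the WHT package, and the available text defines neither the total nor the perspective, while the objective is about adding WHT. If the total is built from the listed categories, a measured saving smaller than the per-patient WHT cost would be reported as a reduction although the net effect is an increase.

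The size cannot be derived from the documents. Every dollar amount and percentage in the working rests on assumed prices and care costs, and only the 240 patients and the 10% drop-out come from the plan. The documents do not support saying that the total excludes WHT as a matter of fact, that the overall contrast is biased towards WHT by a known amount, or that a reported saving would in truth be a loss.

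Cost is not one of the three primary clinical endpoints, so their analysis is unaffected. The change is still worth making, because cost answers a stated objective and the remedy is cheap.

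**What to change.** 1. Define total cost and the costing perspective. Label the listed-category total *medical and pharmacy cost excluding WHT*.
2. Report beside it the same contrast with a per-patient WHT cost added, from a stated unit-cost table covering devices, app and dashboards, and clinician time on alerts. The cost may enter the model or be netted against the estimated mean difference in dollars. Spreading it over quarters inside the gamma model is optional.
3. Base any statement that adding WHT reduces total costs on the inclusive figure. Otherwise limit the conclusion to healthcare costs excluding the intervention.
4. State whether protocol-driven study visits in the WHT group count as outpatient cost.
5. If a fuller protocol or SAP already settles these points, carry the definition into the endpoint wording.

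The price is a small costing exercise, one table, a second reporting line and some SAP wording. No new patients, visits or assessments are needed. The result may be less favourable to WHT.

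### Must the plan name one time contrast to decide each primary comparison, given that its detectable effects rest on an omnibus F test?

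*Combined protocol and SAP*

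**What the plan says.** The Objectives of the Protocol Synopsis ask whether adding the wearable technology "leads to improvements in clinically meaningful patient outcomes". Under Outcome Measures, the first primary endpoint is "A difference in the change in pain scores over time from baseline to month 12 (M12"), and the other two primary endpoints follow the same pattern.

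Sample Size gives 240 WHT, 1000 MPM and 150 historic MPP patients, 10% drop-out and 80% power. It bases the detectable effects on a repeated-measures ANOVA, "using an omnibus F test (difference in changes between the groups at any time"). The effects, versus MPM and versus historic MPP, are 0.35 and 0.42 (NPS), 1.40 and 1.81 (PHQ-8), and 11.51 and 17.58 (MEQs).

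Statistical Methods provides three things:
- "Repeated measures models will be used to generate point estimates and 95% confidence intervals (CIs) for least square mean (LSM) differences";
- "Where appropriate an overall F statistic will be generated to compare the change in groups across the study period (interaction of group*time");
- a choice of model class: "generalized linear modeling or nonparametric methods (depending on the score distributions) will be used to compare outcomes across the cohorts".

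Study Design adds that control data come from the health record: "Assessments will have occurred as part of their standard of care".

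**The concern.** An omnibus F has no direction and is not tied to M12. A worsening, or an early difference that has gone by M12, can make it significant as readily as a sustained benefit. The synopsis qualifies the F as applying where appropriate, plans LSM differences without attaching a visit, and does not say which result decides. It also does not say whether 0.35 on the NPS is a difference at M12, an average over follow-up or something else.

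Two things would be at stake. The result that counts might be chosen after the data are seen, which inflates the false-positive rate. And a reader might take the detectable effects for M12 effects when they are not. Both would matter more than usual in a non-randomized, unblinded comparison with record-based controls.

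**Working it through.** **1. The plan's own figures.** These cannot be reproduced, because alpha, SDs, within-patient correlation and the number of time points are not stated. One check is possible. With a common SD, correlation and set of times, sample sizes alone fix the ratio of the historic-MPP effect to the MPM effect (equal drop-out cancels):

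sqrt[(1/240 + 1/150) / (1/240 + 1/1000)] = 1.45.

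The stated ratios are 0.42/0.35 = 1.20, 1.81/1.40 = 1.29 and 17.58/11.51 = 1.53. Inputs therefore differed between comparisons. That may be legitimate and shows no error.

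**2. The text side by side.** Outcome Measures words the endpoints as change over time. Sample Size powers an F for a difference in change at any time. Statistical Methods plans an F for group-by-time. These are one test described three times. The qualifier on the F can be read as covering outcomes reported as odds or risk ratios, or analysed nonparametrically, where such an F may not exist.

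**3. Compound symmetry.** Assumptions, none from the documents: two-sided alpha 0.05, complete data, large-sample tests, k common post-baseline times ending at M12 (control times are not set, so k = 6, 4, 3, 2). L is the non-centrality that gives the k-df F 80% power. The covariance of the k change scores is proportional to I + J, with inverse I − J/(k+1). For a sustained effect the quadratic form is k − k²/(k+1) = k/(k+1). For an effect at one time only it is 1 − 1/(k+1) = k/(k+1), the same. So the F has 80% power for either pattern and either sign. For a sustained effect the M12 contrast has non-centrality L(k+1)/(2k), and the average has L on 1 df.

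| k | L | M12 non-centrality | M12 power | Average power |
|---|---|---|---|---|
| 6 | 13.62 | 13.62 × 7/12 = 7.95 | 80.5% | 96% |
| 4 | 11.94 | 11.94 × 5/8 = 7.46 | 78.0% | 93% |
| 3 | 10.90 | 10.90 × 4/6 = 7.27 | 76.9% | 91% |
| 2 | 9.63 | 9.63 × 3/4 = 7.22 | 76.7% | 87% |

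Under this pattern the stated effects come close to M12 effects. For a difference at the first time only, M12 power is 5% while the F keeps 80%.

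**4. Correlation that decays with time.** Take first-order autoregressive correlation of 0.9 per two months and k = 2 (months 6 and 12). The correlations are 0.9³ = 0.729 over six months and 0.9⁶ = 0.531 over twelve. The change-score variances are 2(1 − 0.729) = 0.542 and 2(1 − 0.531) = 0.937, with covariance 0.469. The quadratic form for a sustained effect is (0.542 + 0.937 − 2 × 0.469)/(0.542 × 0.937 − 0.469²) = 1.88. The M12 non-centrality is 9.63/(1.88 × 0.937) = 5.47, which gives 65% power. The same calculation for the other cases gives:

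| Correlation | Baseline-to-M12 correlation | M12 power, k = 6 / 4 / 3 / 2 |
|---|---|---|
| Autoregressive 0.9 | 0.53 | 40 / 48 / 55 / 65% |
| Patient intercept 0.4 plus 0.6 × autoregressive 0.8 | 0.4 + 0.6 × 0.262 = 0.56 | 47 / 55 / 61 / 69% |

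A stable patient intercept cancels from change scores, so the second row has the same power as pure autoregressive 0.8, whose baseline-to-M12 correlation is only 0.26. The loss at M12 therefore does not need an implausibly low correlation.

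**5. Choosing among results.** With no true difference and compound symmetry (400,000 draws per k), at least one of F, M12 and average reaches p < 0.05 in 11.3 / 10.6 / 10.2 / 9.0% of trials. Adding every single time point gives 21.9 / 16.9 / 14.0 / 10.5%. With a true sustained benefit, F and M12 disagree in 18.5 / 17.4 / 16.1 / 13.1%.

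**6. Limits of naming one contrast.** It holds 5% only within one comparison. Across three outcomes and two controls, with one contrast each, simulation with 216/900/135 patients and outcome correlation 0 to 0.5 gives about 22% to 24% for at least one p < 0.05.

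**The case for a change.** The strongest case for a change is that no sentence says which result decides, that fixing it costs little more than wording, and that an uncommitted choice among F, M12 and average roughly doubles the 5% error rate within a comparison (9.0% to 11.3%). The factual part stands: the synopsis neither ranks the F against the LSM differences nor says what time point or average its detectable effects refer to.

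The rest carries less weight.
- **Direction** does not separate the tests. A two-sided M12 contrast has the same power for a same-size worsening as for a benefit. With either test, sign is read from the estimates, and the plan already reports those with intervals.
- **The 21.9% figure** supposes an analyst who tests every visit and picks one. Nothing in the plan proposes that.
- **M12 as the deciding contrast** is a preference. It can cost much power for a sustained benefit, and it leans on late control scores recorded at routine-care times. The average does better under compound symmetry but can also fall below the F: 72% with autoregressive 0.9 and six times.
- **The detectable effects** are unlabelled, but none is shown to be wrong.

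The depression endpoint is defined "as measured by the Patient Health Questionnaire (PHQ-9") but its detectable effects are labelled PHQ-8. That label conflict is real and separate. It has no bearing on which contrast decides.

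**Conclusion.** No change follows. The synopsis indicates a legitimate group-by-time F test for the primary outcomes and pairs it with LSM differences and 95% intervals, from which sign and timing can be read. What is unwritten is the order in which these are presented and the time reference of the detectable effects. An analyst would settle that when specifying the output, with the same data and model.

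Prescribing M12 would be a trade-off with no clear gain. Where the F has 80% power for a sustained benefit, M12 has 76.7% to 80.5% under compound symmetry and about 40% to 69% under the decaying correlations tabulated above. It adds no direction, and it leaves the error rate across six comparisons at about 22% to 24%. All of this assumes a two-sided 5% alpha, complete data and common assessment times. The documents give no correlation with which to choose between the patterns. Only a synopsis is available, so any statement that the choice is left open until after the data are seen is conditional on that.

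### WHT versus MPM cannot isolate the effect of adding WHT to the MPP, and the one control group that shares the programme is defined in two ways

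*Combined protocol and SAP*

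**What the plan says.** **Objective** (Protocol Synopsis, Objectives): "To assess whether the addition of WHT to the Geisinger MPP leads to improvements in clinically meaningful patient outcomes".

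**Groups** (Protocol Synopsis, Patient Population):
- WHT: "patients admitted to the MPP during a predefined 12-month period who consented to participate in the study".
- MPM: "patients from MPM clinics within Geisinger during the same 12-month period".
- Historic MPP: "patients who completed the MPP 12 months before the start of this study (ie, before WHT was introduced to the MPP in August 2017").

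The historic group is described again under Study Design, as "patients enrolled in the MPP in the preceding year (historic control group"), and that section says of the WHT group: "Patients consented into the WHT group will participate in the study for 12 months from the day of enrollment".

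**Endpoints** (Outcome Measures, Study Aim 1): there are three unranked primary endpoints. The first is "A difference in the change in pain scores over time from baseline to month 12 (M12) as measured by the Numerical Pain Score (NPS"); the others are depression score and mean daily morphine equivalents (MEQs).

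**Power** (Sample Size): at least 240 WHT, 1000 MPM and 150 historic patients, 10% drop-out, 80% power, and an omnibus F test for a difference in change at any time. The detectable effects are "NPS: 0.35 versus MPM; 0.42 versus historic MPP", and likewise 1.40 and 1.81 for depression and 11.51 and 17.58 for MEQs.

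**Analysis** (Statistical Methods): covariates found to be imbalanced at baseline enter the adjusted models, estimates carry 95% confidence intervals, and a group-by-time F statistic is produced where suitable. No section says which control comparison carries the objective.

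**The concern.** The two controls answer different questions. Only the historic group has the same programme as the WHT group. Any difference between MPP and MPM enters the WHT-versus-MPM estimate one for one, so if the MPP does better than MPM, that contrast can look favourable when WHT contributes nothing. MPM is also the larger control group and has the smaller detectable effect on every primary endpoint. The contrast that is least able to isolate WHT is therefore the one with the most sensitive test.

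The attribution then rests on the historic contrast, whose comparator is unclear. Completers and enrollees are different populations, and the WHT group is formed from people entering the programme. With neither the contrast nor the cohort fixed, both could be settled after results are known.

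**Working it through.** **1. The plan's own figures.** They cannot be reproduced, because the synopsis gives no standard deviation, within-patient correlation, number of time points or alpha. A two-means approximation shows what they imply.
- Sizes after 10% drop-out in every group: 216 WHT, 900 MPM, 135 historic.
- Standard-error factors: sqrt(1/216 + 1/900) = 0.0758 for MPM; sqrt(1/216 + 1/135) = 0.1097 for historic.
- Assumed two-sided 5% and 80% power: 1.960 + 0.842 = 2.802. Implied SD = effect / (2.802 x factor).
- NPS: 0.35/0.2123 = 1.65 and 0.42/0.3074 = 1.37. Depression: 6.59 and 5.89. MEQs: 54.2 and 57.2.
- With a common SD, the historic/MPM ratio of effects would be 0.1097/0.0758 = 1.45. The stated ratios are 1.20, 1.29 and 1.53, so the two columns must rest on inputs specific to each contrast. This does not show that the figures are wrong.

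**2. What each contrast estimates.** Write P for the MPP-versus-MPM difference in change and W for the added effect of WHT within the MPP.
- WHT versus MPM = P + W.
- WHT versus historic MPP = W + calendar trend + selection (the WHT group consented; historic patients are taken from records).

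Every WHT patient is in the MPP and, by inference, no MPM patient is. Programme and WHT are then fully aliased in the first contrast. Adjusting for baseline covariates can reduce differences in case mix, but it cannot separate P from W.

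**3. Size of the attribution problem.** No document gives P, so it is set to a fraction f of the detectable effect with W = 0. For NPS against MPM, f = 0.25, 0.50 and 0.75 means 0.09, 0.18 and 0.26 points.

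The degrees of freedom of the omnibus test are not stated. The calculation uses 1 df and 6 df (six post-baseline WHT visits), with a noncentral chi-square in place of F. Noncentrality for 80% power at 5% is 7.85 (1 df) or 13.62 (6 df). It scales by f squared, if P has the same profile over visits as the powered effect.

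| f | Noncentrality, 1 df / 6 df | P(significant), 1 df / 6 df |
|---|---|---|
| 0.25 | 0.49 / 0.85 | 0.108 / 0.086 |
| 0.50 | 1.96 / 3.41 | 0.288 / 0.231 |
| 0.75 | 4.42 / 7.66 | 0.556 / 0.510 |

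Because f is relative to each endpoint's own detectable effect, the table applies to all three primaries.

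**4. The historic group, side by side.**
- Patient Population: the defining event is completion, dated 12 months before study start.
- Study Design: the defining event is enrolment, in the preceding year.
- WHT group: the defining event is admission, with 12 months counted from enrolment.

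A lenient reading of the dates might bring the first two closer, but it does not remove the completion condition. No baseline date is stated for the historic group.

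Restricting to completers shifts the historic mean change by (share not completing) x (difference in change between completers and non-completers). Neither factor is in the documents. For illustration only, 10% x 0.5 = 0.05 and 30% x 1.0 = 0.30 NPS points, against a detectable 0.42. If completers do better, this shift works against WHT.

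**The case against.** **Two imperfect controls are a sensible design.** One shares the programme and the other shares the period, and each covers a weakness of the other. Listing detectable effects for both is ordinary practice and is not itself a claim about attribution. This stands as a reason to keep the MPM comparison. It does not remove the need to say what each contrast estimates.

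**The sizes are assumptions.** The attribution figures are the power curve read at assumed values of P, and what MPM patients receive is inferred. Both are true, and the figures are conditional on them. The aliasing itself does not depend on the size of P.

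**Contamination.** A reader might infer that historic follow-up is contaminated. With admissions spread evenly over the year before August 2017, half of the patients would reach month 6 and none would reach month 12 before WHT was introduced. The documents do not support the inference: WHT is supplied to consenting patients in the study window, and no section says that historic patients received it. Ending the historic window in July 2016 would also widen the gap between mid-windows from about 12 to about 24 months, which increases exposure to calendar trend.

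**Multiplicity.** A reader might also infer an inflated error rate. Six independent tests at 5% give 1 - 0.95^6 = 26.5%, or about 19-24% allowing for correlation with a common SD. That holds only if any one significant test counts as success, and no text says so. If all must succeed, there is no inflation. The 95% intervals suggest, without stating, a two-sided 5% level. Only a synopsis is available, so a fuller plan may contain a rule.

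**Conclusion.** The concern holds in two parts. First, WHT versus MPM estimates a combined effect, and the synopsis does not say that the objective must be answered through the historic contrast. If WHT adds nothing, the MPM test would still be significant in about 9-11%, 23-29% or 51-56% of trials when the programme difference is 25%, 50% or 75% of the detectable effect. This assumes a two-sided 5% level, 1 to 6 df, and MPM care without MPP or WHT. Second, the historic group has two incompatible definitions, and a completers-only version is selected differently from the WHT group; the size of that effect is unknown.

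The historic contrast is not unconfounded, since calendar trend and consent selection remain. Neither contamination of historic follow-up nor an inflated family-wise error rate is shown by the documents.

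**What to change.** 1. **Name the contrast.** State that WHT versus historic MPP addresses the added effect of WHT, with calendar trend and consent selection as stated limits. Confirm what MPM patients receive. Keep WHT versus MPM as the concurrent comparison, labelled 'combined effect of MPP + WHT versus MPM', with no claim for WHT from it alone.
2. **Define the historic group once, before extraction.** Take all patients admitted to the MPP in one stated pre-study window, whether or not they completed it, with baseline and 12 months counted from admission as in the WHT group. Exclude, or examine in a sensitivity analysis, any patient or follow-up time with documented WHT exposure. Do not move the window back to July 2016 unless such exposure is shown. Restate the detectable effects for the resulting number.
3. **Optional.** If a confirmatory claim is intended, state the alpha and a rule for the three primaries on the historic contrast. Base success on the month-12 least squares mean difference and its confidence interval. A significant omnibus test plus a favourable sign at month 12 is not enough. In simulation, with WHT worse at months 2 to 6 and no effect later (scaled to 80% omnibus power at 5%), that rule declared success on an endpoint in about 33% of trials at alpha 0.0167. This is roughly 0.66 power times a one-half chance of a favourable sign.

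**Cost.** Items 1 and 2 need revised wording and a redefined record extraction, with no new enrolment. The claim from the MPM contrast becomes narrower. The historic number may change: if 100 or 180 remained instead of 135 (illustrative values), the NPS effect would become 0.42 x 1.102 = 0.46 or 0.42 x 0.920 = 0.39, using sqrt[(1/216 + 1/n)/(1/216 + 1/135)]. If item 3 is taken up with a first-step alpha of 0.05/3 = 0.0167, detectable effects rise by 13-15% (NPS 0.47-0.49 at n = 135), and power at the stated effects falls to about 66% at that step.
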